3.5.4 Data management and analysis

Sample Size for Pilot For the feasibility pilot, we will plan to enroll 154 adolescents who are due for an HPV vaccine dose. With a minimal sample size of 77 in each arm, we will be powered to detect a hazards ratio of 1.67 with 80% power, allowing for a 5% type I error comparing time to next dose.

At the study sites, we expect there to be, on average, 1074 girls aged 10-14 in need of vaccination over a 4-month period. We expect 913 families to meet age, language and cell phone/texting inclusion criteria. To meet our minimal sample size of 154 (77/arm) for this pilot/feasibility study, we need to recruit 16.9% of eligible families, which is feasible. If recruitment is slower than expected, we will be able to use more KCCA sites.

Data Management

Vaccination data will be abstracted from the HPV vaccination registers in use clinically at the sites. Girls generally seek care from one site. All data will be entered into a REDCap database hosted at Columbia with secure access provided only to Columbia and Ugandan study staff. The Ugandan-based project coordinator will monitor text messages sent, replies, and "undeliverable" messages under the supervision of Drs. [name] and [name]. Linkages between parents' and girls' information, survey data and vaccine records will be maintained in separate password protected files. All final datasets will be coded.

D10. Analytic Plan

The primary analytic plan for the pilot will focus on feasibility of implementation of the

intervention using a RE-AIM implementation framework (Reach, Effectiveness, Adoption, Implementation, Maintenance). We will focus only on reach, effectiveness, and implementation (not adoption or maintenance which is not applicable for this pilot).

Reach: We will collect data on number of families

- approached
- eligible and ineligible (including reasons for ineligibility)
- eligible who enrolled
- number enrolled in text message vs. phone reminders

Effectiveness: While the focus of the pilot is on feasibility, we will also assess the effect size of the intervention. The outcome will be timeliness of vaccination (time to event). Time will be from start of main message series to receipt of the next needed dose. Data analysis will be performed using Stata. The primary analysis will be intention-to-treat (ITT), whether or not further messages were declined or undeliverable. A secondary per protocol analysis will only include those who received the entire set of reminders. Timeliness of vaccine receipt will be compared using Kaplan-Meier curves using a stratified log rank test. In addition, in order to gain effect sizes needed for a future large-scale intervention, comparisons will also be stratified assessing those due for the first dose (initiation) and second dose (completion).

Implementation: We will assess various process measures, including:

- Messages sent/delivered (if a text message is electronically returned as undeliverable, we will contact the family using alternative numbers that will be collected at enrollment)
- Number who opted out of further messages
- Number who responded to messages
- Topics families request more information about in reminders
- Factors associated with response and drop out
 - child characteristics (age, site, school status (in or out of school), grade, relationship with caregiver)
 - family characteristics (age, education, employment, income, marital status, distance to health facility, language)

We will also randomly select 30 intervention parents from whom we have received permission in the consent to re-contact. We will conduct a semi-structured interview that will focus on
Page 24 of 142

intervention experiences and suggested changes, and follow the methods and analytic plan outlined under Aim 1. We will also have them complete two implementation measures: Acceptability of Intervention Measure (AIM), Intervention Appropriateness Measure (IAM). These were developed and psychometrically assessed by implementation scientists as consensus measures for *acceptability* and *appropriateness*. In addition, they will also complete an adapted Health Information Technology (IT) Usability Evaluation Scale (Health-ITUES). We will then present findings to key non-parental stakeholders (as identified under Aim 1) and conduct semi-structured interviews to gather feedback. Conduction of the interviews and the analytic plan will follow the methods outlined in Aim 1.

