2.0 Literature Review

Completion rates of HPV vaccination in Uganda are low. The national HPV vaccination program in Uganda began in November 2015,¹⁴ and targets girls who are 10 years old.¹⁵ In Kampala, the *school-based* program is to be delivered during every health facility and outreach immunization session, but intensified during Child Days Plus- month-long outreach sessions held two times a year in April and October, or whichever months they will be held during the course of the study. The *community-based* program occurs throughout the year at health facilities- overseen by city authorities or health institutions.

Not all adolescents who receive the first dose of HPV vaccine receive the second dose they need to complete the series. Furthermore, of those who do receive the second dose, many do not receive it within the recommended 12 months, resulting in more days at risk. In two previous national surveys, 72% and 83% of girls assessed initiated vaccination, but only 39% and 27% of them, respectively, completed the series.¹⁶ While coverage rates have gone up in some areas of Uganda, in Kampala City currently only 29% of girls in the target age range have received two doses of the vaccine.¹⁷ Similarly, at an adolescent clinic (*study site*) in Kampala, of the girls aged less than 14 years old who initiated vaccination between November 2015 and July 2017, only 30.2% completed the series within 6 months and 36.5% within 12 months—and only 69.8% completed the series at all.¹⁸ At three local health centres and affiliated schools (*study sites*), average completion rates are even lower, ranging from 10.5% to 40.5% of those who initiated.¹⁷ The current rate of completion HPV2 is 12%.¹⁹

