We have established strong evidence supporting HPV vaccine text message reminders. [name] (MPI of the grant) published the first studies using text message vaccine reminders for adolescent and pediatric populations.³⁴⁻⁴⁰ In addition, she has previously identified the effectiveness of HPV vaccine text message reminders in two studies. In the first, caregivers whose child received a first or second dose of the HPV vaccine received a series of text message reminders when the next dose was due. Adolescents whose caregivers were texted were more likely to receive their next dose on-time vs. non-enrollees (51.6% of enrollees vs. 35.0% of nonenrollees [p = 0.001] or 38.1% of historical controls [p=0.003]).⁴⁰ In a secondary analysis (unpublished), those receiving text messages also had higher series completion rates (45% vs. 29% p<0.01). These *conventional* reminders solely notified caregivers via text that the next dose was due; they did not include any other information such as vaccination-related educational health information. While these results strongly supported the potential effectiveness of text message reminders, still fewer than half of adolescents (45%) completed the series. In her most recent study, [name] demonstrated 74.1% completion rates of HPV vaccine series within 12 months for adolescents of caregivers receiving text message reminders.⁴¹ This rate was much higher than both historical controls (34.8%) and the comparison group of non-enrollees (45.2%, p<0.0001).

This proposed project is innovative in four important ways.

 This will be the *first use* of text message vaccine reminders for *adolescent* vaccinations in not only Africa but for any LMIC. Text message vaccine reminders have been used for *pediatric* vaccination studies in Africa in Kenya and Nigeria^{33,42-45} and three other non-African LMICs,⁴⁶⁻⁴⁸ but not for *adolescent* vaccines including HPV. While on the surface it may seem that the use of mHealth interventions for adolescent vaccination does not differ from that of pediatric vaccination, that is not true. Adolescent vaccination patterns, knowledge and perceptions do differ from that of pediatric vaccination, and interventions in high and low-middle income countries also differ.⁴⁹ Therefore, text message performance cannot be extrapolated from those targeted to caregivers of young children or to caregivers in high-income settings.

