We will enroll only one child per family; if more than one is eligible, one will be randomly selected. For the pilot feasibility trial, we will enroll families of girls who are in need of either the first or second dose, with an outcome of receipt of next needed dose. Due to the need to complete the pilot feasibility trial quickly, we will only enroll those in need of the second dose if their next dose is due strictly between 8-20 weeks from enrollment. We will seek written consent from caregivers. We will seek written assent from adolescents of consented caregivers given instead. At enrollment, parents will be verbally administered a demographic and HPV vaccination knowledge and attitude survey.

After enrollment, the Ugandan project coordinator will randomize families into intervention vs. usual care arms (1:1 ratio) stratified by enrollment site, parental language (English or Luganda), and dose due (1st or 2nd) using a randomization module. Research staff will not know the study assignment during enrollment. The outcome assessor and analyst will remain blinded to arm assignments.

Families who report on the demographic survey their highest degree of schooling as P7 or below will be asked at enrollment if, in the case they are randomized to the intervention, they would prefer a voice reminder in lieu of texts; such reminders would include the same content, timing and interactivity as the texts. While in Kampala only 2.1% of women and 0.5% of men have no formal education, 17.6% of women and 17.1% of men completed only some primary school.31 Similarly, families whose daughter is returning to a boarding school and are enrolled at the Adolescent Clinic, health centres, or immunization post will be asked if, in the case they are randomized to the intervention, they want messages sent timed for the next school break. Alternatively, they can select the timing used for those not at boarding school. If the special timing is selected, we will account for the minimal interval between doses (for those in need of a second dose). Intervention-arm families enrolled through Child Days Plus will be sent their series prior to the next Child Days Plus event at their child's school or before any other special immunization day events, if the school holds one.

Intervention, Text Message Target, Content and Frequency:

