For those families randomized to the intervention arm: Based on our previous studies as well as the full country HPV vaccine evaluation highlighting the parents involvement as vaccine decision makers, we plan for the messages to be targeted to the parent, unless in Aim 1 families suggest that girls should also receive the message. All text messages are automated and will be sent in English or Luganda based on parental preference.

The message sequence consists of 5 weekly, main message reminders beginning 5 weeks before the

HPV vaccine dose due date, followed by a series of 2 primary booster messages.(Figure 3). This is based on our previous studies that showed that the median number of messages needed to come in for a vaccine was 5. If enrollment happens more than 4 weeks before the main messages are due to

start, engagement messages will be sent monthly until main messages start. The due date for the vaccine will depend on whether the first (initiation) or second

(completion) dose is due and the enrollment site.

For those who need to initiate vaccination and are:

- *Recruited as part of the school-based program*, the due date will be defined as the next Child Days Plus
- *Recruited in health centre and not in boarding school*, the due date will be defined as 5 weeks after message initiation
- *Recruited in health centre and are in boarding schools,* the due date will be the next school break
- *Recruited in the community*, the due date will be defined as the next HPV vaccination day at the community immunization post that is at least 5 weeks after message initiation

For those who need to complete the vaccination series and are:

- *Recruited as part of the school-based program*, the due date will be defined as the next Child Days Plus
- *Recruited in health centre and not in boarding school*, the due date will be defined as 6 months after the date of the first dose (which is the recommended interval between doses)
- *Recruited in health centre and are in boarding schools,* the due date will be the next school break that is a least 5 months after the date of the first dose, which is the minimal allowed interval between doses
- *Recruited in the community*, the due date will be defined as the next HPV vaccination day at the community immunization post that is at least 5 months after the date of the first dose

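### 80% power for a hazard ratio of 1.67 with 77 per arm needs about 120 vaccinations (78% of 154) in 6 months; no event rate is stated, and the closest study-site rate (36.5%, second dose), applied to all girls, gives about 69 vaccinations and 57% power

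*Protocol*

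**What the plan says.** The sample-size paragraph in Protocol section 3.5.4 plans 154 girls and states: "With a minimal sample size of 77 in each arm, we will be powered to detect a hazards ratio of 1.67 with 80% power", with a 5% type I error, for time to next dose. It does not give a usual-care vaccination rate, a required number of events, a dose mix or the sidedness of the test. The SAP has no sample-size section.

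Follow-up is 6 months per girl (Protocol 3.5.3; SAP, Primary Analysis). The clock starts with the main messages (Protocol 3.5.4, Effectiveness). The trial is mixed by dose: "we will enroll families of girls who are in need of either the first or second dose" (Protocol 3.5.3).

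The background rates are in Protocol section 2.0. At the adolescent clinic, a study site, among girls who had started the series, "only 30.2% completed the series within 6 months and 36.5% within 12 months" and "only 69.8% completed the series at all". The three health centres and their affiliated schools range from 10.5% to 40.5%, with no time limit given. Earlier text-message studies by one of the investigators reported on-time receipt of "51.6% of enrollees vs. 35.0% of nonenrollees [p = 0.001] or 38.1% of historical controls", and comparator series completion of 34.8% and 45.2%. None of these rates is linked to the power statement.

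**The concern.** A log-rank test draws its power from events. The same 154 girls can give high or low power depending on how many are vaccinated before censoring, so a power figure without an event rate cannot be checked. The rates the protocol does cite are mostly far below what 80% needs.

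This matters because effect size determination is listed as a feasibility milestone (Abstract, Methods), and section 3.5.4 wants effect sizes for a later large-scale intervention. A reader who believes the pilot had 80% power could take a non-significant result as evidence against the reminders, when the estimate may simply be imprecise.

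**Working it through.** **Inputs.** 77 per arm, 1:1 allocation, hazard ratio (HR) 1.67, 80% power, 5% type I error and 6 months of follow-up, all from the documents. My assumptions: a two-sided test, proportional hazards and no dropout.

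**Step 1. Events needed (Schoenfeld).**

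d = 4(1.960 + 0.842)² / (ln 1.67)² = 119.4, so 120 vaccinations. 120/154 = 78%.

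Freedman's formula gives 124.6, so 125. If all 154 girls were vaccinated, power would be only 89%, so 80% leaves little room for non-uptake.

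**Step 2. Uptake that yields those events.** With usual-care uptake p0, intervention uptake is p1 = 1 − (1 − p0)^1.67, and expected events are 77(p0 + p1). Setting this to 119.4 gives p0 = 69.1% and p1 = 85.9%.

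**Step 3. Reproducing the plan's figure.** With p0 = 69.8%, the clinic's completion rate with no time limit, p1 = 86.5%, events = 120.3, power = 80.3% and the required size is 76.4, i.e. 77 per arm. No other completion rate cited as background does this. That the planners used it is an inference. The same sentence puts completion at 36.5% by 12 months, so 69.8% does not fit a 6-month window.

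**Step 4. Which rate is closest.** For a health-centre girl not in boarding school, "the due date will be defined as 6 months after the date of the first dose" (about week 26), and the series is "5 weekly, main message reminders beginning 5 weeks before the" due date. Her follow-up starts at week 26 − 5 = 21 (month 4.8) and ends 6 months later, at month 10.8. The 12-month rate of 36.5% is therefore the nearest available. If anything it is generous, because it also counts girls who completed before this window opened.

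**Step 5. Power by usual-care rate, applied to all girls.** Power = Φ(½√d · ln 1.67 − 1.96).

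| Usual-care uptake | Source (Protocol 2.0) | Events | Power |
|---|---|---|---|
| 10.5% | health centres and schools, lowest | 21 | 22% |
| 30.2% | clinic, within 6 months | 58 | 50% |
| 34.8% | comparator, completion | 66 | 55% |
| 35.0% | comparator, on-time | 66 | 55% |
| **36.5%** | **clinic, within 12 months** | **69** | **57%** |
| 38.1% | comparator, on-time | 72 | 58% |
| 40.5% | health centres and schools, highest | 76 | 61% |
| 45.2% | comparator, completion | 84 | 65% |
| 69.8% | clinic, no time limit | 120 | 80% |

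For 36.5%: p1 = 1 − 0.635^1.67 = 53.2%, and 77 × (0.365 + 0.532) = 69.0 events. A log-rank simulation with 8,000 replicates gave power of 0.491 at 30.2%, 0.555 at 36.5% and 0.810 at 69.8%.

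**Step 6. What 69 events can show.** The HR detectable with 80% power at 36.5% is about 1.93 (73 events at that HR). The 95% confidence interval is the estimate multiplied and divided by exp(1.96 × 2/√d): about 1.60 at 69 events, against 1.43 at 120.

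**Step 7. How far first-dose girls could help.** Hold second-dose uptake at 36.5%.

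- Minimum first-dose share, if every first-dose girl is vaccinated: (119.4 − 69.0)/(154 − 69.0) = 59.3%.
- Half first-dose, all of them vaccinated: 77 + 34.5 = 111.5 events, 77% power.
- 75% first-dose: 80% power needs 82.4% usual-care first-dose uptake within 6 months.

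**Step 8. One-sided test.** This needs 94.0 events (95 rounded up), or 51.7% usual-care uptake. At 36.5%, power is 69%.

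**The case against.** The strongest objection is that no printed number has been shown to be wrong: 77 per arm and 80% agree with each other at about 69% usual-care uptake, and the 57% comes from applying a second-dose rate to a sample that includes first-dose girls. The protocol also cites national initiation of 72% and 83%. As an illustration, use those for first-dose girls and 36.5% for second-dose girls. Half first-dose then gives 96 to 103 events and 71% to 74% power; 75% first-dose gives 110 to 120 events and 77% to 80%. The month 5 to 11 match also covers only one recruitment route, since school, community and boarding-school girls have other due dates.

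Much of this stands. The exact shortfall is unknown, and 57% is one conditional value. But the initiation rates are national and have no time limit, so they are not 6-month usual-care uptake, and they reach 80% only with the higher rate and about three-quarters first-dose girls. The text states no such mix. The Objective 3 flow diagram was not available to me, so I cannot exclude that it shows one. The health-centre and school range, which has no time limit either, points lower, at 22% to 61%.

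It is also fair that feasibility is the pilot's main focus. That limits the consequence but does not support the stated 80%.

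**Conclusion.** The concern holds. The 80% is stated without conditions, and the time-limited completion rates in the protocol do not deliver it when applied to all girls: they give 50% to 65%, with 57% at the closest study-site rate. These figures assume HR 1.67, 154 girls, a two-sided 5% test, proportional hazards and no dropout. Power near 80% is possible with a large first-dose share and high first-dose uptake. A one-sided test would lower the bar to 94 events, but the documents support assuming neither. The point should be fixed. It is moderate, because the pilot is mainly about feasibility and the sample size need not change.

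**What to change.** Keep 154 girls and replace the power sentence in Protocol section 3.5.4 with a conditional statement, the sponsor filling the blanks:

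> With 154 girls, 80% power for a hazard ratio of 1.67 (two-sided 5%) requires about 120 vaccinations within 6 months of the start of main messages. We assume usual-care uptake of __% in first-dose and __% in second-dose girls, with __% needing the first dose, giving __ expected vaccinations and __% power. At the study clinic's 12-month second-dose rate (36.5%) in all girls, we would expect about 69 vaccinations and 57% power, and the hazard ratio detectable with 80% power is about 1.9. The hazard ratio with its 95% confidence interval will be reported as the pilot's effect estimate.

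If a one-sided test was intended, say so and restate the events. The national initiation rates of 72% and 83% should not be entered as 6-month uptake.

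The cost is wording in the protocol and a short SAP addition naming the model for the hazard ratio and its interval, since neither document specifies one. No extra participants are needed. The sponsor has to commit to uptake and dose-mix assumptions, and the stated power becomes conditional and probably lower.

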Messages will focus on when/where to go for the next dose, and will include educational information identified in Aim 1. Messages will be different for those who need the first dose (initiation) and 2nd dose (completion). We will also include an interactive text message allowing participants to ask for and receive more information according to their specific needs, and receive an automated response with information on that subject. For those still unvaccinated, booster

messages will be sent bi-weekly for one month and then monthly until the end of the 6 month observation period for each individual during the pilot trial. Sites will be visited every 2-4 weeks to abstract data; we will stop messages for those already vaccinated. HPV registers for schools are generally kept with the affiliated KCCA health centre immunization nurses. For families of those unvaccinated who were first vaccinated at Child Days Plus will receive booster messages directing them to bring their daughter to the KCCA health centre affiliated with their school (who conducts their Child Days Plus outreach) as they will have missed the school vaccination day.

Usual Care arm: Families randomized to the *usual care arm* will not receive text message vaccine reminders.

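### The secondary per-protocol rule selects intervention girls partly on when they were vaccinated, because messages stop after vaccination, and the set of messages it requires is undefined

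*Protocol*

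**What the plan says.** The effectiveness outcome is time from the start of the main messages to the next needed dose, and the primary analysis is intention-to-treat (ITT) (protocol 3.5.4; SAP, Primary Analysis). Both documents then add the same sentence: "A secondary per protocol analysis will only include those who received the entire set of reminders". Neither defines the set or says how usual-care families enter this analysis.

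Protocol 3.5.3 describes the messages. "The message sequence consists of 5 weekly, main message reminders beginning 5 weeks before the" vaccine due date, "followed by a series of 2 primary booster messages". Further boosters are conditional on the outcome: "For those still unvaccinated, booster" "messages will be sent bi-weekly for one month and then monthly until the end of the 6 month observation period". The stopping rule is explicit: "we will stop messages for those already vaccinated". Stopping can lag behind the dose, since "Sites will be visited every 2-4 weeks to abstract data". Usual-care families "will not receive text message vaccine reminders".

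**The concern.** How many reminders an intervention girl receives depends on when she is vaccinated, and that time is the outcome. A rule requiring a full set therefore selects on the outcome in one arm only. Read literally, no usual-care girl qualifies. The ITT sentence, which keeps families who declined messages or could not be reached, suggests that the per-protocol set was meant to remove only those families and to leave usual care intact, but neither document says so.

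A per-protocol result is naturally read beside the ITT result as the effect in families who actually got the reminders, and this pilot is partly meant to supply effect sizes for a larger trial. Under the present wording the same data can give a per-protocol result that is too low, about right or too high, depending on the definition the analyst chooses.

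**Working it through.** The rule carries no figure of its own, so there is nothing to reproduce. The sample-size HR of 1.67 with 77 per arm (protocol 3.5.4) serves only as the assumed true effect.

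**Inputs from the documents.** HR 1.67; 77 per arm; 6 months of follow-up, taken as 26 weeks; 5 weekly main messages, then 2 boosters; register visits every 2 to 4 weeks, taken as a stopping lag of 0 to 4 weeks; control risk 30.2% (protocol 2.0). That last figure is second-dose completion within 6 months at one clinic, so it is only a rough proxy.

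**Assumptions.** All usual-care girls kept. Constant hazard, starting either at the first main message (week 0) or at the due date (week 5). Main messages in weeks 0 to 4 and the second booster in week 8 or 9.

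**Set = 5 main + 2 boosters.** A girl is kept if vaccination time plus lag reaches the last booster. Hand calculation for the relative risk at 26 weeks, hazard from week 0:
- Control cumulative hazard: −ln(1 − 0.302) = 0.360. Intervention: 1.67 × 0.360 = 0.600, so risk 1 − exp(−0.600) = 0.451. True relative risk: 0.451/0.302 = 1.49.
- Last booster week 9, no lag. Dropped: 1 − exp(−0.600 × 9/26) = 0.188, or about 14 of the 35 intervention vaccinations (77 × 0.451). Risk among those kept: (0.451 − 0.188)/0.812 = 0.324. Relative risk: 0.324/0.302 = 1.07.
- Last booster week 8, lag 4 weeks. Dropped: 1 − exp(−0.600 × 4/26) = 0.088, or about 7. Risk among those kept: (0.451 − 0.088)/0.912 = 0.398. Relative risk: 1.32.

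Large-sample simulation gives these Cox HRs (true value 1.67) at lags of 0/2/4 weeks:

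| Required set | Vaccination from week 0 | Vaccination from week 5 |
|---|---|---|
| 5 + 2, last booster week 8 | 1.09/1.22/1.37 | 1.39/1.57/1.67 |
| 5 + 2, last booster week 9 | 1.02/1.15/1.29 | 1.30/1.48/1.67 |
| 5 main only | 1.37/1.52/1.67 | 1.67/1.67/1.67 |

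Replacing 30.2% by 10.5% to 40.5% (protocol 2.0, which gives no time window for that range) changes the 5 + 2 results little: 0.99 to 1.39 from week 0 and 1.28 to 1.68 from week 5.

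**Set = every message due while unvaccinated.** Here an early vaccinee has fewer messages to miss. Take messages in weeks 0 to 4, 6, 8, 12, 16, 20 and 24, and let each fail independently, after any retry, with probability q. A girl with m messages due is kept with probability (1 − q)^m. A girl never vaccinated has 11 due, so at q = 5% she is kept with probability 0.95^11 = 0.57. Vaccinated intervention girls are kept 71% of the time (true HR 1.67, week 0, no lag). With **no true effect**, HRs at q = 2/5/10% are:
- from week 0: 1.07/1.21/1.50 with no lag; 1.05/1.13/1.30 with a 4-week lag;
- from week 5: 1.05/1.14/1.32 with no lag; 1.04/1.09/1.21 with a 4-week lag.

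If instead non-delivery is a property of the family, unrelated to vaccination, early and late vaccinees are excluded alike and the HR is 1.00 at every rate. With failures strongly clustered within families (assumed correlation 0.8, week 0) it is 1.00/1.01/1.01.

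**Precision.** ITT events: 77 × (0.302 + 0.451) = 58, so the 95% interval spans a factor of exp(1.96 × 2/√58) = 1.67 each way. The 5 + 2 set (week 0, last booster week 9, no lag) has 58 − 14 = 44 events, factor about 1.81. The messages-due set has about 37 to 54 events (true HR 1.67), factor about 1.90 to 1.70.

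**The case against.** The strongest reply is that this is one secondary analysis in a feasibility pilot with an ITT primary, and that sampling error exceeds most of these biases. Both points are true and they set the severity. They do not remove the defect, since an interval does not cover selection on the outcome.

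Second, the set may mean only the 5 main messages. The protocol reserves the word main for those and times the outcome from them. That reading is plausible, and under it there is no bias if nobody is vaccinated before the due date. But it is not written down, and bias remains if girls can be vaccinated earlier and messages stop promptly.

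Third, a reader might infer that any failed message tilts the messages-due version towards the reminders. The documents do not support that. They say nothing about whether failures are independent, and a family-level failure such as a dead number produces no bias. Protocol 3.5.4 also has staff try alternative numbers. If 2/5/10% were rates before one independent retry, the null HRs would fall to about 1.00/1.01/1.04 (week 0). The 1.07/1.21/1.50 figures are therefore upper-end illustrations.

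Fourth, neither document plans a Cox model. They plan Kaplan-Meier curves, a stratified log-rank test, chi-square tests and a relative risk. The HR here is a convenient scale, and the relative risks above show the same distortion.

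Nothing should be read into the absence of a per-protocol item from the SAP's five numbered analyses: that list also omits ITT and the log-rank test.

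**Conclusion.** The concern holds as a minor one. Confidence is high on the mechanism, which follows from section 3.5.3 alone, and moderate on size, which rests on an assumed constant hazard, a proxy control risk and assumed message timing.

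With 5 main plus 2 boosters the bias runs against the reminders: a true HR of 1.67 becomes about 1.02 to 1.37, and a relative risk of 1.49 becomes about 1.07 to 1.32, if vaccination can occur from week 0; the HR is 1.30 to 1.67 if only from the due date. With the 5 main messages alone the HR is 1.37 to 1.67, or unbiased from the due date. With messages due while unvaccinated, bias towards the reminders is possible but depends on failures occurring message by message.

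Two stronger conclusions might be drawn and are not supported. The trial's main result is not compromised, because ITT does not use this rule. Nor should a reversed effect be expected: HRs of about 0.1 to 0.5 arise only if boosters up to week 24 are required, an unlikely reading.

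**What to change.** In protocol 3.5.4 and the SAP, define the set without reference to vaccination:
- keep all usual-care girls;
- exclude an intervention girl only if her first main message (text or voice) reached no number on file, counting retries made before the second main message is due, or if her family opted out before the second;
- never exclude a girl because vaccination ended her messages;
- label the result exploratory.

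Dropping the per-protocol analysis would serve equally well.

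The cost is a sentence or two in each document; delivery, alternative-number and opt-out data are already to be collected. The drawback is that the set will be close to ITT and no longer measures receipt of the full series. Some confounding also remains, because non-delivery and opt-out are not randomised. As an assumed example, let 20% of families have half the vaccination hazard and three times the non-delivery. At 2/5/10% base non-delivery, the rule then excludes 3/7/14% of intervention girls and gives HRs of 1.00/1.01/1.02 with no true effect. With a quarter of the hazard and five times the non-delivery, the HRs are 1.01/1.04/1.08.
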